## 13.11 Follow Up of Subjects after AE

The staff of the clinical facility has to monitor the clinical trial subject's safety from the occurrence of an AE until satisfactory recovery.

Any AE which remains unresolved at the time point of subject's last visit requires detailed evaluation and follow-up until the AE has been resolved or a reasonable explanation for its persistence is found; in case of AEs related to the IMPs every effort has to be made to follow-up clinical trial subjects in order to determine the final outcome. If follow-up cannot be completed until release of CRF by the investigator the individual CRF will be released and transferred to the Clinical Data Management. In this case, follow-up information will be documented separately in the subjects' record and outcome including a short description on follow-up procedures performed must be sent to the sponsor.

It is the investigator's responsibility to assure that subjects experiencing adverse reactions will receive definitive treatment for any adverse reaction, if required. Details of follow-up care are to be provided (i.e. if treatment or hospitalization is required). The responsibility to provide adequate follow-up for AEs includes periodically repeating laboratory tests yielding clinically abnormal results at the end of study evaluation.

## 14.0 ETHICS

This study will be performed in accordance with the ethical principles that have their origin in the current Declaration of Helsinki and will be consistent with International Conference on Harmonization Good Clinical Practice (ICH GCP) and applicable regulatory requirements. The study will be conducted in compliance with the protocol.

The rights, safety and well-being of the study subjects are the most important considerations and should prevail over interests of society and science.

## 14.1 Informed Consent

The Investigator must ensure that study subjects are clearly and fully informed about the purpose, potential risks and other critical issues regarding clinical studies in which they volunteer to participate. The principles of Informed Consent, according to FDA Regulations and ICH GCP will be followed. A copy of the proposed consent form must be submitted to the IRB, together with the protocol, for approval. Prior to beginning of the study, the Investigator must have the IRB's written approval of the written informed consent form and

any other information to be provided to study subjects.

Informed consent will be obtained from all study subjects using the following procedure: Study subjects must have provided IEC/IRB approved written informed consent. Each study subject's signed informed consent must be kept on file by the Investigator. A copy of the signed consent form will be given to the study subject. A notation will be made in the study subject's medical record indicating the date the informed consent was obtained. In addition, the Investigator or the Investigator's Designee will provide a HIPAA authorization form (if applicable) for the study subject to review and sign. Both the ICF and the HIPAA form (if applicable) must be signed by the study subject before any protocol assessments can be undertaken.

## 14.2 Institutional Review Board

Before study initiation, the Investigator must have, including but not only, written and dated approval from the IEC/IRB for the protocol, consent form, study subject recruitment materials and any other written information to be provided to study subjects. The Investigator or Actavis LLC/CRO will also provide the IRB with a copy of the package insert.

Any changes to the protocol as well as a change of the Investigator, which is approved by the Sponsor, must also be approved by the site's IRB and documentation of this approval provided to the Sponsor/designee. Records of the IRB review and approval of all documents pertaining to this study must be kept on file by the Investigator and are study subject to inspection during or after completion of the study. All SAEs must also be reported to the IRB.

Periodic status reports must be submitted to the IRB at least annually, as well as notification of completion of the study and a final report within one (1) month of study completion or discontinuation. A copy of all reports submitted to the IRB must be sent to the Sponsor/designee.

## 14.3 Study Subject Confidentiality

As of April 14, 2003, the federal medical Privacy Rule authorized by the Health Insurance Portability and Accountability Act (HIPAA) requires most health care providers to take new measures to protect the privacy of individually identifiable health information. The Privacy Rule's requirements extend to identifiable health information used or disclosed in research.

The HIPAA Privacy Rule reinforces clinical Investigators' existing obligations to protect the privacy of identifiable health information under state law, codes of medical ethics and the federal regulations governing research.

Please be advised that the Privacy Rule compliance obligations include the following:

- 1. Treating individually identifiable health information as confidential in accordance with HIPAA and other federal, state and local laws and regulations governing the confidentiality and privacy of such information
- 2. Using or disclosing individually identifiable health information for study subject

recruitment purposes only as permitted by HIPAA, applicable laws and regulations and institutional policies

- 3. Obtaining each study subject's written authorization for the use or disclosure of individually identifiable health information in research, where applicable, in a form that meets the requirements of HIPAA and identifies all uses, disclosures and data recipients
- 4. Disclosing identifiable health information created or maintained in connection with the research only for the purposes and to the parties described in the authorization form or as necessary to communicate with the Food and Drug Administration and other regulatory authorities or as otherwise permitted or required by law
- 5. Employing appropriate physical and technical safeguards to protect the privacy of individually identifiable health information
- 6. Obtaining a HIPAA waiver of authorization, or where applicable, providing representations and/or entering data use agreements as required under the HIPAA Privacy Rule for any secondary data analyses or activities preparatory to research and referencing these and other research uses and disclosures in your HIPAA notice of privacy practices.

Also, in compliance with federal guidelines regarding the monitoring of clinical studies and in fulfillment of his/her obligations to the Sponsor, it is required that the Investigator permit the study monitor, Sponsor auditor, IRB and/or FDA representative to review that portion of the study subject's medical record that is directly related to the study. This shall include all study relevant documentation including study subject medical histories to verify eligibility, admission/discharge summaries for hospital stays occurring while the study subject is enrolled in the study and autopsy reports for deaths occurring during the study.

As part of the required content of the informed consent, the study subjects must be informed that his/her medical chart may be reviewed by the Sponsor, the Sponsor's authorized representatives, FDA officials. Should access to the medical record require a separate waiver or authorization, it is the Investigator's responsibility to obtain such permission from the study subject in writing before the study subject is entered into the study.

## **15.0 DOCUMENTATION**

## 15.1 Site Regulatory Documents Required for Initiation

A minimum of the following set of documents will be received by the CRO prior to the initiation of the study:

- 1. Fully executed protocol
- 2. Completed and signed FDA Form 1572
- 3. Current curricula vitae, signed and dated for the Investigator and each Sub-Investigator named in the FDA Form 1572 (current within 2 years)
- 4. Current medical licenses of the Investigator and Sub-Investigators named in FDA Form 1572
- 5. Documentation of "No Objection" to proceed from the local regulatory agency, wherever applicable.
- 6. Documentation of IRB approval of this study protocol, Investigator and informed consent forms

- 7. Current IRB membership list or roster and EC SOPs
- 8. Original Non-disclosure Agreements for the Investigator and Sub-Investigators named in FDA Form 1572
- 9. Financial Disclosure Statement for the Investigator and each Sub-Investigator named in FDA Form 1572
- 10. Sites Clinical Laboratory Head's current (within 2 years) curricula vitae and normal reference ranges of laboratory parameters
- 11. Fully executed Clinical Trial Agreement

## 15.2 Maintenance and Retention of Records

It is the responsibility of the Investigator to maintain a comprehensive and centralized filing system of all relevant documentation.

Copies of all pertinent records will be retained by the Investigator for at least two years following final approval of the drug and/or notification from the Sponsor. These regulatory documents should be retained for a longer period if required by local regulatory authorities. These records include documents pertaining to the receipt and return of drug supplies, IEC/IRB, informed consent, source documents, as well as CRFs (paper or electronic files). No documents shall be transferred from the site or destroyed without first notifying the Sponsor. The Sponsor will archive the data for the lifetime of the product. If the Investigator withdraws from the study, the records shall be transferred to a mutually agreed upon designee. Notice of such transfer will be given in writing to the Sponsor.

The Investigator is required to prepare and maintain adequate and accurate case histories designed to document all observations and other data pertinent to the investigation on each individual treated with the investigational product or entered as a control in the investigation. Data reported on the eCRF, which are derived from source documents, must be consistent with the source documents.

## **15.3** Case Report Forms (CRFs)

Electronic Data Capture (EDC) technology will be utilized. Electronic CRFs (CRFs) will be prepared for all data collection fields. Study subjects will be identified by initials, birth date and subject number, if applicable. Corrections to the CRF will generate an automated audit trail including date and timestamp, full name of the person making the correction and original entry. The user will document the reason for the change which is also maintained in the audit trail. CRFs may be reviewed and signed manually / electronically by properly trained and authorized individuals. The EDC platform will be compliant with 21 CFR part 11 security and audit trail requirements.

CRFs must be kept current to reflect the study subject's status at each phase during the course of the study. Study subjects are not to be identified on CRFs by name; appropriately coded identification (i.e., study subject study number) and the study subject's initials must be used. The Investigator must keep a separate log of the study subject's names and addresses.

Source documents such as the clinic chart are to be maintained separately from the e- CRF (in order to allow data verification. Due to the potential for errors and inaccuracies in entering data into CRFs, originals of laboratory and other test results must be kept on file with the study subject's source document. Source documents and copies of test results must be available at all times for inspection by the study monitor.

## 15.4 Primary Source Documents

The Investigator must maintain primary source documents supporting significant data for each study subject's medical notes. These documents, which are considered "source data", should include documentation of:

- Demographic information
- Evidence supporting the diagnosis/condition for which the study subject is being studied
- General information supporting the study subject's participation in the study
- General history and physical findings
- Hospitalization or Emergency Room records (if applicable)
- Each study visit by date, including any evaluations, relevant findings/notes by the Investigator(s), occurrence (or lack) of adverse events and changes in medication usage, including the date the study drug commenced and completed.
- Any additional visits during the study
- Any relevant telephone conversations with the study subject regarding the study or possible adverse events
- An original, signed informed consent form for study participation
- Subject Diary

The Investigator must also retain all study subject specific printouts/reports of tests/procedures performed as a requirement of the study. During monitoring visits, the monitor will need to validate data in the CRFs against these sources of data.

## 15.5 Study Monitoring

will be responsible for monitoring the study according to Good Clinical Practice and applicable regulations. Monitoring visits are for the purpose of confirming adherence to the protocol and to verify complete and accurate data collection. The clinical site will make all records associated with the study available to representative during such visits and audits.

The study may be subject to audit by the Sponsor, Sponsor Representative or by regulatory authorities. If such an audit occurs the Investigator must agree to allow access to required patient records. By signing this protocol, the Investigator grants permission to personnel from the Sponsor, its representatives and appropriate regulatory authorities for on-site monitoring of all appropriate study documentation, as well as on-site review of study procedures.

The following should also be available for review:

- 1. Study Subject Screening Log reflecting the reason any study subject screened for the study was found to be ineligible
- 2. Delegation of Authority / Study Personnel Signature Log all site personnel will be listed along with their responsibilities and signatures; to be maintained at the site throughout the study
- 3. Monitoring Log the date and purpose of all monitoring visits by the Sponsor/Designee will be documented
- 4. Enrollment Log documenting study subject initials and start and end dates for all study subjects enrolled
- 5. Drug Inventory/Packing Slip reflecting the total amount of drug shipped to the site and received and signed for by the Investigator
- 6. Drug Accountability Log reflecting the total amount of investigational product dispensed to and returned by each study subject
- 7. Informed Consent Form which must be available for each study subject and be verified for proper documentation
- 8. All correspondence

Monitoring visits will be arranged in advance at a mutually acceptable time with site personnel. Sufficient time must be allowed by the site personnel for the monitoring of CRFs and relevant source documents. The Study Coordinator and/or Investigator should be available to answer questions or resolve data clarifications. Adequate time and space for these visits should be made available by the Investigator.

At the end of the study, a closeout monitoring visit will be performed.

# 15.6 Audits and Inspections

During the course of the study and/or after it has been completed, one or more site visits may be undertaken by auditors as authorized representatives of the Sponsor. The purpose of the audit is to determine whether or not the study is being conducted and monitored in compliance with the protocol, recognized GCP guidelines and all applicable regulations. Additionally, the study may be inspected by regulatory agencies. These inspections may take place at any time during the study or after the study.

# 15.7 Modifications to the Protocol

The procedures defined in the protocol and in the eCRF/paper CRF will be carefully reviewed to ensure that all parties involved with the study fully understand the protocol. In order to ensure the validity of the data, no deviations from the protocol, with minimal exceptions, may be made unless the issue is broad enough to warrant revision of the protocol. Such revisions must be submitted to and have documented approval from the Sponsor and the IEC/IRB prior to implementation. All amendments to the protocol, which involve substantial changes in study design, procedure or analyses, will be submitted to appropriate regulatory authority for prior approval.

The only circumstance in which an amendment may be initiated without prior IEC/IRB approval is to eliminate apparent immediate hazards to a study subject or study subjects. However, the Investigator must notify the Sponsor and the IEC/IRB as soon as possible.

## 15.8 Completion of Study

The Investigator is required to forward CRFs and all other relevant data and records to CRO. The Investigator will complete and report (submission of CRFs) his/her study in satisfactory compliance with the protocol as soon as possible after the completion of the study.

The Investigator must submit a final report to the IEC/IRB and CRO within one (1) month of study completion or discontinuation.

## 16.0 CONFIDENTIALITY, USE OF INFORMATION AND PUBLICATION

All information supplied by the Sponsor in connection with this study and not previously published, is considered confidential information. This information includes, but is not limited to, data, materials (i.e., the clinical protocol, CRFs), equipment, experience (whether of a scientific, technical, engineering, operational or commercial nature), designs, specifications, know-how, product uses, processes, formulae, costs, financial data, marketing plans and direct selling systems, customer lists and technical and commercial information relating to customers or business projections used by the Sponsor in its business. Any data, inventions or discoveries collected or developed, as a result of this study is considered confidential. This confidential information shall remain the sole property of the Sponsor, shall not be disclosed to any unauthorized person or used in any unauthorized manner without written consent of the Sponsor and shall not be used except in the performance of the study.

The information developed during the course of this clinical study is also considered confidential and will be used by the Sponsor in connection with the development of the drug. The information may be disclosed as deemed necessary by the Sponsor. To allow the use of the information derived from this clinical study, the Investigator is obliged to provide the Sponsor with complete test results and all data developed in the study. The information obtained during this study may be made available to other Investigators who are conducting similar studies.

## **APPENDIX I: SCHEDULE OF EVENTS**

Visit Details	Visit 1	Telephone Call	Visit 2	Visit 3	Visit 4	Visit 5
Study Activities	Day -21 to -1 Screening/ Baseline/ Randomization	Day -1 Pre-Operative Telephone Call	Day 0 The Day of Cataract Surgery	Day 1 One Day After Cataract Surgery	Day 7 + 2 days Follow-up visit	Day 14 + 2 days (End of Study / Early Discontinuation)
Informed Consent Process	×					
Medical History & Demographics	×					
Pre-Operative Call		×				
Physical Examination	×					×
Vital Signs	×		×	×	×	×
Inclusion/Exclusion Review	×					
Schedule the day for Cataract Surgery	×					
Assessment of Ocular Pain	×			×	×	×
Visual Acuity	×				×	×
Slit Lamp Examination	×			×	×	×
Intraocular Pressure	×			×	×	×
Fundus Examination	×					×
Laboratory Assessments (hematology, biochemistry and urine analysis)	×					×
Urine Pregnancy Test	×		×			×
Dispense/Administer Study drug	×		×	×	×	×
Dispense Subject Diary	×			×	×	
Retrieval/Review of Subject Diary					×	×
Retrieval of Study Medication						×
Concomitant Medication Assessment	×		×	×	×	×
Adverse Event Assessment	×	×	×	×	×	×

## **APPENDIX II: INSTRUCTIONS FOR THE SUBJECT**

- 1. The proper way to instill the drop-in eye is detailed in your subject diary. The study medication should be applied in the operative/operated eye as one drop once daily for 16 days starting from a day before the surgery, continued on the day of surgery and then 2 weeks thereafter. On Day 0 a drop should be added 30-120 minutes prior to the cataract surgery. As the study drug will be administered twice on the day of cataract surgery (day 0) once prior to cataract surgery and once following cataract surgery prior to the subject leaving the surgery center. The study is designed to be only monocular (only one eye per subject).
- 2. During Visit 2, administration of drug should only be performed by the patient, caregiver, independent study drug administrator or unmasked site personnel that are not assigned any other study duties. At your visit today, you were instructed how to use study medication.
- 3. How to apply the eye drops: Shake the bottle well just before you use it. To apply the eye drops:
  - a. Tilt your head back slightly and pull down your lower eyelid to create a small pocket. Hold the dropper above the eye with the dropper tip down. Look up and away from the dropper as you squeeze out a drop and then close your eyes.
  - b. Gently press your finger to the inside corner of the eye (near your nose) for about 1 minute to keep the liquid from draining into your tear duct or gently close eyes for 15-30 seconds.
  - c. Do not allow the dropper tip to touch any surface, including the eyes or hands. If the dropper becomes contaminated it could cause infection in your eye, which can lead to vision loss or serious damage to the eye.
  - d. At least 5 minutes between all ophthalmic drop administrations should be maintained throughout the study.
- 4. You have to complete the subject diary after each instillation in the eye. You will be allowed to take acetaminophen as needed for ocular pain. You will record any use of acetaminophen in your subject diary. Adults and Adolescents Weighing 50kg and Over: 1,000mg every 6 hours or 650mg every 4 hours to a maximum of 4,000mg per day. Minimum dosing interval of 4 hours. Adults and Adolescents Weighing under 50kg: the recommended dosage of acetaminophen injection is 15 mg/kg every 6 hours or 12.5 mg/kg every 4 hours, with a maximum single dose of acetaminophen injection of 15 mg/kg, a minimum dosing interval of 4 hours, and a maximum daily dose of acetaminophen of 75 mg/kg per day. A minimum of 8 hours between the last dose of acetaminophen and assessment of ocular pain and aqueous cells and flare should be maintained.
- 5. Do not use any other ophthalmic treatments or start any new medications during your study participation without prior approval from your study doctor.
- 6. If you miss any dose during the study on a day, then continue the instillation as directed from the next day on.
- 7. Avoid any contact with affected eye during your day-to-day activities.
- 8. Slow or delayed healing may occur while using the study medication.
- 9. Please avoid allowing the tip of the bottle to touch your eye or surrounding structures because this could contaminate the tip and cause infection. Serious damage to the eye and subsequent loss of vision may result after using such contaminated solution.
- 10. If you develop any condition like infection, are thinking of having ocular surgery, or suffer trauma you should contact your study doctor right away.
- 11. Do not use the eye drops when wearing contact lens.
- 12. For Visit 3 (Post-Op Day 1), please follow the Subject Diary's instructions for the Subject to administer the study medication at the doctor's office following your exam.
- 13. On Visit 4 and Visit 5, the study medication will be administered prior to visiting the site for scheduled

assessments at respective visits.

- 14. It is important that you bring your study medication with you at each visit in order to determine if you are using the study medication properly. You will be given additional bottles, if needed. All used and unused study medication must be returned to your doctor's clinic during Visit 5.
- 15. If you see a doctor for another medical problem while you are participating in the study, please have him/her call your physician.
- 16. The study coordinator will attempt to remind you of your next scheduled visit.

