#### **Diagnosis/Target Population and Key Inclusion Criteria:**

Study will be conducted on subjects who have a clinical diagnosis of cataract and are planning to undergo cataract surgery.

The study is designed to be only monocular (only one eye per subject).

Other inclusion and exclusion criteria are mentioned in sections 4.2 and 4.3 of the protocol.

Sponsor:	Name of Medical Products:	Active Ingredient(s):
Actavis LLC	Nepafenac and Ilevro ™ (Nepafenac ophthalmic	Nepafenac
	suspension)	
Investigational P	oducts:	
TEST PRODUC	Т:	
Name of the prod	uct: Nepafenac	
1	osage form: Ophthalmic suspension	
Strength: 0.3%		
Manufactured by:	Actavis LLC.	
REFERENCE P	RODUCT:	
Name of the proc	uct: Ilevro TM (Contains Nepafenac)	
Pharmaceutical d	osage form: Ophthalmic suspension	
Strength: 0.3%		
Manufactured by:	Alcon Laboratories, Inc	
-		
PLACEBO:		
Name of the prod	uct: Sterile ophthalmic suspension	
Pharmaceutical de	osage form: Ophthalmic suspension	
Strength: NA		
U U		
Manufactured by:	Actavis LLC.	

A drop of the study drug suspension should be instilled into the affected eye one-time daily, beginning a day prior to the planned cataract surgery, on the day of the cataract surgery and for 14 days thereafter. The study drug should be instilled once daily. On the day of cataract surgery (Day 0) a drop should be added 30-120 minutes prior to the surgery and once following cataract surgery prior to the subject leaving the surgery center.

Note: As the study drug will be administered twice on the day of cataract surgery (Day 0) once prior to cataract surgery and once following cataract surgery prior to the subject leaving the surgery center. The dose and mode of treatment chosen in this study is the dosage approved by US FDA for the treatment of pain and inflammation associated with cataract surgery.

At least 5 minutes between all ophthalmic drop administrations should be maintained throughout the study.

Clinical Evaluations will be performed at:

- Visit 1: Day -21 to Day -1 (Screening/Baseline/Randomization Visit) Pre-Operative Call: Day -1
- Visit 2: Day 0 (The Day of Cataract Surgery)
- Visit 3: Day 1 (One Day After Cataract Surgery)
- Visit 4: Day 7± 2 Days (Follow-up Visit)
- Visit 5: Day 14 ± 2 Days (End of Study Visit/ Early Discontinuation)

Sponsor:	Name of Medical Products:	Active Ingredient(s):
Actavis LLC	Nepafenac and Ilevro ™ (Nepafenac ophthalmic	Nepafenac
	suspension)	

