#### 8.4 Visit 4: Follow-up Visit (Day $7 \pm 2$ Days)

- 1. Review the subject diary to assess for any adverse events, changes in concomitant medication & compliance to study drug.
- 2. Retrieve the subject diary pages for completed visit and keep in the source file of the patient
- 3. Vital signs
- 4. Assessment of ocular pain
- 5. Visual acuity assessment
- 6. Slit Lamp Examination
- 7. Assessment of Intraocular pressure
- 8. Re-dispense the subject diary to the subject with instructions to document the administration of the study drug, adverse events, and any concomitant medication

used. Also, the patient should be instructed to administer the study medication before visiting the clinical facility for next scheduled visit.

9. Schedule Visit 5

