#### **11.6 Administration of Investigational Product**

One drop of the study drug suspension should be instilled into the affected eye one-time daily, beginning a day prior to the planned cataract surgery, on the day of the cataract surgery and for 14 days thereafter. The study drug should be instilled once daily. On Day 0 a drop should be added 30-120 minutes prior to the cataract surgery. As the study drug will be administered twice on the day of cataract surgery (Day 0) once prior to cataract surgery and once following cataract surgery prior to the subject leaving the surgery center. On Day 0 administration of drug should only be performed by the patient, caregiver, independent study drug administrator or unmasked site personnel that are not assigned any other study duties. The dose and mode of treatment chosen in this study is the dosage approved by US FDA for the treatment of pain and inflammation associated with cataract surgery. The study is designed to be only monocular (only one eye per subject).

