#### 5.3 Corneal Effects

Use of topical NSAIDs may result in keratitis. In some susceptible patients, continued use of topical NSAIDs may result in epithelial breakdown, corneal thinning, corneal erosion, corneal ulceration or corneal perforation. These events may be sight threatening. Patients with evidence of corneal epithelial breakdown should immediately discontinue use of topical NSAIDs including ILEVROTM (nepafenac ophthalmic suspension), 0.3% and should be closely monitored for corneal health.

Postmarketing experience with topical NSAIDs suggests that patients with complicated ocular surgeries, corneal denervation, corneal epithelial defects, diabetes mellitus, ocular surface diseases (e.g., dry eye syndrome), rheumatoid arthritis, or repeat ocular surgeries within a short period of time may be at increased risk for corneal adverse events which may become sight threatening. Topical NSAIDs should be used with caution in these patients.

Postmarketing experience with topical NSAIDs also suggests that use more than 1 day prior to surgery or use beyond 14 days post-surgery may increase patient risk and severity of corneal adverse events.

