7.8.9 Exposure to Product

The subjects will be instructed to use the diary to document all doses taken. Additionally, the dose taken one day prior to the surgery will be recorded on the eCRF.

Compliance with scheduled application of IP will be determined from the subject's diary as $[\text{Actual number of doses}] / [\text{Planned number of doses}] * 100\%$, where

- Actual number of doses will counted from the subject diary and relevant eCRF pages;
- Planned number of doses is 17 (i.e. Days -1 through Day 14 with two doses taken on Day 0).

Number of missed doses will be calculated as the number of planned dosing time-points when the study drug was not taken during the 16 days starting with the date of the first dose. There is one dosing time-point per each day, except the day of Visit 2 Day 0, when there are two planned time-points, before the surgery and after the surgery.

Subjects who missed dosing for more than 3 consecutive days will be considered non-compliant and will be excluded from the PP population.

Subjects can be additionally excluded from the PP population due to non-compliance, if the Investigator's and Sponsor's review of their dosing times suggests a clinically meaningful departure from the once-daily dosing pattern.

Subjects will be considered compliant if they administer at least 14 doses and not more than 20 doses, with no more than 3 consecutive missed dosing days. The compliance will be analyzed using the descriptive statistics by treatment group. The proportion of compliant vs. non-compliant subjects will be tabulated for each treatment.

Duration of exposure will be calculated as Date of last use of the study drug – Date of first use of the study drug + 1. Duration of exposure will be summarized descriptively by treatment group.

Compliance, number of doses and duration of exposure will be summarized for the Safety and mITT populations.

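### The instruction to take study drug before Visit 5 is not reconciled with a course ending on Day 14, although Visit 5 may fall on any day from Day 12 to Day 16

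*Protocol*

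**What the plan says.** **Length of the course.** Protocol 11.6 sets dosing as "beginning a day prior to the planned cataract surgery, on the day of the cataract surgery and for 14 days thereafter". The synopsis gives the treatment duration as 16 days. Item 1 of the subject instructions in Appendix II describes the drop "as one drop once daily for 16 days starting from a day before the surgery". SAP 7.8.9 states: "Planned number of doses is 17 (i.e. Days -1 through Day 14 with two doses taken on Day 0").

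**Dosing around Visit 5.** Appendix II item 13 says: "On Visit 4 and Visit 5, the study medication will be administered prior to visiting the site for scheduled" assessments. Protocol 8.4 item 8, carried out at Visit 4, says that "the patient should be instructed to administer the study medication before visiting the clinical facility for next scheduled visit"; the next scheduled visit is Visit 5. The schedule of events (Appendix I) puts a mark at Visit 5 in a combined row for dispensing or administering study drug.

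**The visit window.** The synopsis lists "Visit 5: Day 14 ± 2 Days (End of Study Visit/ Early Discontinuation"), so Day 12 to Day 16 is permitted. Protocol 8.5 has the container collected at Visit 5, and Appendix II item 14 has all medication returned then.

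**Compliance.** Protocol 9.0 and 11.7 and SAP 7.8.9 treat fewer than 14 or more than 20 doses as non-compliant. The SAP counts missed doses over 16 days from the first dose. It takes the actual number of doses from the diary and eCRF and states no last day.

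**Label text.** Appendix III, which Protocol 13.4 names as the reference safety information, says in its section 5.3 that postmarketing experience with topical NSAIDs suggests that "use beyond 14 days post-surgery may increase patient risk and severity of corneal adverse events".

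**The concern.** The course length is tied to the day of surgery, while the last pre-visit dose is tied to the date of Visit 5. The two agree only when Visit 5 falls on Day 14. For a visit on Day 15 or 16, a subject who follows item 13 literally goes past the 16 days that item 1 of the same sheet gives. For a visit on Day 12 or 13, the bottle is handed in before the 14 post-operative days are complete.

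Three things are at stake:

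- **Safety wording.** Some subjects could be dosed for a day or two in the period that the attached label warns about, on an instruction given by the protocol itself.
- **Reporting.** Protocol 13.10 requires any administration not in accordance with the protocol to be recorded on the CRF. With the present text, a site cannot tell whether a Day 15 dose is as instructed or reportable.
- **Exposure and compliance.** The SAP divides every subject's doses by 17. A subject who follows the pre-visit instruction exactly can therefore score above or below 100%, depending only on the visit date.

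**Working it through.** **Inputs**

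- Doses: one on Day -1, two on Day 0, then one per post-operative day (Protocol 11.6, SAP 7.8.9).
- Planned total: 17 (SAP 7.8.9). Stated duration: 16 days (synopsis, Appendix II item 1).
- Visit 5: Day 12 to Day 16 (synopsis, Appendix I).
- Compliance range: 14 to 20 doses (Protocol 11.7, SAP 7.8.9).

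**Formulas.** Let L be the last day on which a dose is taken, with no dose missed.

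- Calendar dosing days = L - (-1) + 1 = L + 2
- Doses = 1 + 2 + L = L + 3

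**The plan's own figure.** With L = 14, calendar days = 14 + 2 = 16 and doses = 14 + 3 = 17. Both match the documents.

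**Daily dosing up to and including the day of Visit 5**

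| Visit 5 | Calendar days | Doses | Doses / 17 | Days past Day 14 | Within 14 to 20? |
|---|---|---|---|---|---|
| Day 12 | 14 | 15 | 88.2% | 0 | yes |
| Day 13 | 15 | 16 | 94.1% | 0 | yes |
| Day 14 | 16 | 17 | 100.0% | 0 | yes |
| Day 15 | 17 | 18 | 105.9% | 1 | yes |
| Day 16 | 18 | 19 | 111.8% | 2 | yes |

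**Does the upper compliance limit catch it?** Twenty doses are reached when L + 3 = 20, that is, with daily dosing to Day 17, which lies outside the visit window. No fully adherent subject seen within the window is flagged.

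**Does any text settle the conflict?** Items 1 and 13 of Appendix II were read side by side, together with Protocol 8.4, 8.5, 11.6 and 11.7, Appendix I and SAP 7.8.9. None says that the dose before Visit 5 applies only if the visit is on or before Day 14. None says what to do about remaining doses if the visit is on Day 12 or 13. Protocol 8.5 lists collection of the container but no administration step.

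**The case against.** The strongest reply is that the texts can be read together. Item 13 follows item 12, which has the Visit 3 drop given at the office after the examination. Item 13 may therefore say only when on a visit day the drop is taken, with duration left to item 1 and Protocol 11.6. On that reading a subject stops at Day 14 and takes no drop before a later visit. The reading is plausible, but it is stated nowhere, and the instruction in Protocol 8.4 carries no day limit. Appendix II also refers subjects to the diary for dosing instructions. The diary is not among the documents and may show a last dosing day.

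Several stronger conclusions might be inferred and are not supported:

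- **That the label ties the 14-day course itself to corneal harm.** The warning concerns use beyond 14 days. It rests on postmarketing experience with topical NSAIDs, says only that risk may increase, and gives no figure for one or two extra drops.
- **That Appendix I orders a dose before Visit 5.** It shows one mark in a combined row and gives no order of events.
- **That two of five window days means two fifths of subjects.** The documents give no distribution of visit dates.
- **That the primary comparisons are biased.** The instruction and window are the same in all three randomized, masked arms. Some dependence of response on visit date comes with any ±2-day window.
- **That extra dosing would go unseen.** SAP 7.8.9 summarizes number of doses, percentage compliance and duration of exposure. The 14 to 20 range is a tolerance band and was not designed to police the last dosing day.

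These points limit the size of the problem. They do not remove the gap in the text.

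**Conclusion.** The inconsistency is real and should be corrected. The stated course ends on Day 14 with 17 doses. The pre-visit instruction, read literally, gives 18 doses for a Day 15 visit and 19 for a Day 16 visit. With daily dosing up to a Day 12 or 13 visit, collection of the drug ends dosing at 15 or 16. All of these totals pass the compliance range.

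The counts assume no missed doses and one drop daily up to and including the day of Visit 5. The conclusion that some subjects would go past Day 14 also assumes that sites and subjects take item 13 and Protocol 8.4 literally and that the diary does not say otherwise. How many subjects this affects cannot be known from the documents.

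The case rests on clear instructions, on consistency with the protocol's own reference safety text, and on dose counting. It does not rest on any demonstrated effect on the equivalence or superiority results.

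**What to change.** Reconcile Protocol 8.4 item 8, Appendix II item 13 and the Visit 5 mark in Appendix I with the synopsis duration, Protocol 11.6, Appendix II item 1 and SAP 7.8.9, and with the Visit 5 window. All should say the same about dosing when Visit 5 falls before or after Day 14. If item 13 is meant only as time-of-day guidance, the text should say so. Which rule applies is for the sponsor's clinical team to decide, with the label wording in Appendix III in view. Check the subject diary against the result.

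Once that is settled, align SAP 7.8.9: the planned number of doses used as the denominator, the period over which actual and missed doses are counted, and the compliance rule.

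The cost is wording in the protocol, the subject instructions and the SAP, with the sponsor and IEC/IRB approval that Protocol 15.7 requires for a revision. The correction does not itself require a change to the primary endpoint, the randomization or the sample size.
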